3.6.9 Study withdrawal criteria

The following criteria should determine the immediate withdrawal of the volunteer from the study:

- Grade 2 or greater kidney abnormalities at any time of follow-up.
- Clinical indication to start a drug with significant interactions with TDF/FTC during the development of the study.
- Presentation of any serious adverse event related to the intervention, defined by the physicians assigned to the study.
- Any Adverse Event (AE) that determines that the volunteer wishes to interrupt the intervention.
- That the volunteer voluntarily and for any reason decide to withdraw from the study.

If any of the previously mentioned criteria are met, the doctor assigned to the study in charge of the follow-up will immediately inform the coordinator of their respective center. The report of all AE will be made by the principal investigator of each center, in accordance with the INVIMA regulations and taking into account the Standardized Operating Procedures (SOP) established by the study.

In the event that the patient withdraws their consent, no additional monitoring will be possible. This situation will be reported immediately to the clinical monitor and monthly to the Institutional Research and Ethics Committee (CIEI).

3.6.10. Follow-up of volunteers with a positive pregnancy test at the end of follow-up

Despite the fact that TDF/FTC is a classification B drug in pregnancy, and its use is recommended as one of the antiretrovirals of choice in pregnant women with HIV (76), within this study it was defined to exclude pregnant women, or with the desire to become pregnant, to avoid exposure to this drug given its high placental transfer to the fetus.

There is no evidence in humans of teratogenicity with TDF/FTC, however there is evidence in monkeys, at doses twice as high as the therapeutic doses in humans, of decreased fetal growth and reduced fetal bone porosity within two months of initiation of maternal therapy; Regarding human studies, there is no demonstrated relationship with low birth weight, but there are conflicting results on the outcome of growth in childhood (77).

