The hazard ratio will be estimated by comparing the risk of infection in the intervention group (TDF/FTC + EPP), with the risk in the control group (placebo + EPP), with a confidence interval of 95 %, using a univariate Cox regression model.

If necessary, adjustment will be made for variables that may affect the occurrence of the primary outcome and that are not balanced between the intervention group and the placebo group; The need for adjustment with an OR greater than 1.5 will be considered for dichotomous categorical

variables, such as sex; or if there are differences between the groups greater than 0.25 of the standard deviation for continuous variables such as age, adherence to pharmacological intervention or EPP, and hours of exposure to the COVID area. For the calculation of the adjusted hazard ratio, a multivariate Cox proportional hazards model will be used, if the proportionality assumption is met, or an extended Cox model if this assumption is not met.

For secondary outcomes

-The proportion of incidence of total adverse effects in each group will be determined at day 60 after randomization, estimated as the cumulative incidence using the Kaplan Meier method.

The hazard ratio ("Hazard Ratio") will be estimated by comparing the risk of adverse events in the intervention group (TDF/FTC + EPP), with the risk in the control group (placebo + EPP), with a confidence interval of 95%, using a univariate Cox regression model.

Additionally, the same analysis will be performed for serious adverse events.

- The proportion of incidence of discontinuation of the intervention in each group, for any reason, will be determined at day 60 after randomization, estimated as the cumulative incidence using the Kaplan Meier method.

The hazard ratio will be estimated by comparing the discontinuation of the intervention in the intervention group (TDF/FTC + EPP), with the risk in the control group (placebo + EPP), with a confidence interval of 95 %, using a univariate Cox regression model.

- It will be determined as the difference in the mean or median (according to the distribution of the data) of the percentage in which the individuals were adherent

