Gallant JE et al. In a randomized clinical trial comparing efavirenz (EFV) plus TDF/FTC (N = 257) vs EFV plus zidovudine (AZT) / lamivudine (3TC) (N = 254) for the management of HIV infection in 511 Subjects over 18 years of age, for 144 weeks, reported the following adverse reactions: dizziness (8%), diarrhea (7%), nausea (8%), fatigue (7%), headache (5%), depression (4%), insomnia (4%), skin rash (5%) (93).

Reported laboratory abnormalities included: amylase greater than or equal to 132 (17%), triglycerides greater than 400 mg / dL (13%), neutrophils less than 1000 (7%), hematuria (9%), AST greater than 109 in men or 86 in women (8%), ALT greater than 91IU / L in men or 86 IU / mL in women (7%) (93). However, in this study TDF/FTC was accompanied by EFV, which explains several of the adverse effects, especially psychiatric ones, and skin rash.

More recently, the safety and risk profile of TDF/FTC adverse reactions has been studied in clinical studies of HIV pre-exposure prophylaxis (PrEP) in monotherapy. Grohskopf A. et al. Conducted a clinical experiment to evaluate the safety of a daily dose of TDF in HIV-uninfected subjects for 24 months. The study drug was initiated by 373 (93%) volunteers (186 TDF and 187 placebo), of whom 325 (87%) completed the final study visit. Of 2428 adverse effects (AE) reported among 334 (90%) volunteers, 2366 (97%) were of mild or moderate severity. The frequencies of commonly reported AE did not differ significantly between the TDF and placebo arms. In multivariate analyzes, back pain was more likely among TDF recipients (P = 0.04), these reports were not associated with documented fractures or other objective findings. There was no grade ≥ 3 creatinine elevations, and grade 1 and 2 creatinine elevation were not associated with TDF reception. The estimated percentage of adherence was 92% per pill count. (94).

The Partners PrEP study recruited 4,758 couples, of which 4,747 were followed, 1,584 randomly assigned to TDF, 1,579 to TDF-FTC, and 1,584 to placebo. The rate of serious adverse events at 36

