Laboratory abnormality	Mild (Grade 1) **	Moderate (Grade 2)	Severe (Grade 3)	Potentially Life Threatening (Grade 4)	Death (Grade 5)
Laboratory					
ALT and AST	>3 x ULN if baseline was normal. 1.5-3 x ULN of baseline if it was not normal.	>3-5 x ULN if baseline was normal. >3-5 x ULN of baseline if it was not normal.	>5-20 x ULN if baseline was normal. >5-20 x ULN of baseline if it was not normal.	>20 x LSN ULN if baseline was normal. >20 x ULN of baseline if it was not normal.	
Hemoconcentration	Rise of 0-2 g/dl from baseline.	Rise of 2-4 g/dl from baseline.	Rise of > 4 g/dl from baseline.		
Anemia	Hb<ULN-10g/dl	Hb<10-8g/dl	Hb<8g/dl	Life Threatening; Medical	Death

				intervention is required.	
Lymphocytes Decrease - cell/mm³	< 800/mm ³ ; < ULN - 0.8 x 10e9/L	<800 - 500/mm ³ ; <0.8 - 0.5 x 10e9 /L	<500 - 200/mm ³ ; <0.5 - 0.2 x 10e9 /L	<200/mm ³ ; <0.2 x 10e9 /L	
Neutrophils Decrease - cell/mm³	<LLN - 1500/mm ³ ; <LIN - 1.5 x 10e9 /L	<1500 - 1000/mm ³ ; <1.5 - 1.0 x 10e9 /L	<1000 - 500/mm ³ ; <1.0 - 0.5 x 10e9 /L	<500/mm ³ ; <0.5 x 10e9 /L	
Platelets Decreased - cell/mm³	<LLN - 75,000/mm ³ ; <LLN - 75.0 x 10e9 /L	<75,000 - 50,000/mm ³ ; <75.0 - 50.0 x 10e9 /L	<50,000 - 25,000/mm ³ ; <50.0 - 25.0 x 10e9 /L	<25,000/mm ³ ; <25.0 x 10e9	
Creatinine – mg/dL	Rise of 1.5x ULN	Rise of 1.5 – 3x from baseline; 1.5 – 3 x ULN	Rise of 3x ULN from baseline.; 3 – 6 x ULN	Rise of 6x ULN	

ULN: Upper limit of normal range. LLN: Lower limit of the normal range.

Table 5. Causation of adverse events. Taken from the Common Terminology Criteria for Adverse Events (104,105).

Imputed causation	Definition
Definitive	A clinical event, or alterations in laboratory tests, that manifests with a plausible temporal sequence in relation to the administration of the drug, and that cannot be explained by the concurrent disease, or by other drugs or substances. The response to drug withdrawal (withdrawal; dechallenge) must be clinically plausible. The event must be definitive from a pharmacological or phenomenological point of view, with a conclusive re-exposure (rechallenge).
Probable	A clinical event, or alterations in laboratory tests, that manifests with a reasonable time sequence in relation to the administration of the drug, that is unlikely to be attributed to the concurrent disease, or to other drugs or substances, and that when withdrawing the drug presents a clinically reasonable response. Information on re-exposure is not required to assign this definition.

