Diastolic blood pressure	Quantitative/discrete	Diastolic blood pressure	Diastolic blood pressure in mmHg
Creatinine	Quantitative/continuous	Serum creatinine concentration (mg/dl).	Serum creatinine concentration (mg/dl).
Creatinine rise	Qualitative/nominal	Severity of creatinine rise	0-Normal 1-Grado 1 2-Grado 2 3-Grado 3 4-Grado 4
IgG for SARS-CoV-2	Qualitative/dichotomous	Result of serology test for SARS-CoV-2 (only for follow-up 2)	0- Negative 1- Positive
Data to be collected in follow-up 3			
Platelets	Quantitative/discrete	Number of platelets in complete blood count (CBC)	Number of platelets per microliter (Cels/ μ l).
Thrombocytopenia	Qualitative/nominal	Severity of thrombocytopenia	0-Normal 1-Grade 1 2-Grade 2 3-Grade 3 4-Grade 4
Hemoglobin (Hb)	Qualitative/continuous	Hemoglobin concentration in CBC	Hb (g/dl).
Anemia	Qualitative/nominal	Classification of severity of anemia	0-Normal 1-Grade 1 2-Grade 2 3-Grade 3 4-Grade 4
Lymphocytes	Quantitative/discrete	Number of lymphocytes in complete blood count (CBC)	Number of lymphocytes per microliter (Cels/ μ l).
Lymphopenia	Qualitative/nominal	Classification of severity of lymphopenia	0-Normal 1-Grade 1 2-Grade 2 3-Grade 3 4-Grade 4
Neutrophils	Quantitative/discrete	Number of neutrophils in complete blood count (CBC)	Number of neutrophils per microliter (Cels/ μ l).
Neutropenia	Qualitative/nominal	Classification of severity of neutropenia	0-Normal 1-Grade 1 2-Grade 2 3-Grade 3 4-Grade 4
Aspartate aminotransferase (AST)	Quantitative/continuous	AST concentration in international units per liter (UI/l)	AST (UI/l).
Aspartate aminotransferase elevation	Qualitative/nominal	Severity of elevation of AST	0-Normal 1-Grade 1 2-Grade 2 3-Grade 3 4-Grade 4
Alanine aminotransferase (ALT)	Quantitative/continuous	ALT concentration in international units per liter (UI/l)	ALT (UI/l).
Alanine aminotransferase elevation	Qualitative/nominal	Severity of elevation of ALT	0-Normal 1-Grade 1 2-Grade 2 3-Grade 3 4-Grade 4

Pregnancy test	Qualitative/dichotomous	Applicable only to women. Result of quantitative serum Beta-HCG test regarding upper reference value for non-pregnant women.	0- Negative 1- Positive
RT-PCR SARS-CoV-2	Qualitative/dichotomous	Detection of SARS-CoV-2 by RT-PCR de	0- Undetectable 1- Detectable
Data to be collected only in Follow-up 4			
Follow-up date	Quantitative/continuous	Follow-up date	Day/month/year

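### Two wording errors in the creatinine grading row: Grade 3 does not pick up at 3 x baseline, and Grade 1 has no range of its own

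*Combined protocol and SAP*

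**What the plan says.** The creatinine row of the laboratory table in section 6.3 (the first of two tables numbered 5) reads:

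- Grade 1: "Rise of 1.5x ULN"
- Grade 2: "Rise of 1.5 – 3x from baseline; 1.5 – 3 x ULN"
- Grade 3: "Rise of 3x ULN from baseline.; 3 – 6 x ULN"
- Grade 4: a rise of six times ULN.

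Creatinine is the only kidney measure in that table, and no other section restates its cut-offs. The grade is used in two places. Section 3.6.9 (Study withdrawal criteria) requires immediate withdrawal for "Grade 2 or greater kidney abnormalities at any time of follow-up". Appendix 3 records "Severity of creatinine rise" as a code from 0 to 4, next to the measured value in mg/dL.

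Section 4 analyses adverse events in total, and again for serious events: "The proportion of incidence of total adverse effects in each group will be determined at day 60 after randomization". It plans no analysis by grade.

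**The concern.** A severity scale should never give a lower grade to a larger rise in the same person. Here the Grade 2 limb based on baseline stops at 3 x baseline, and the Grade 3 limb that mentions baseline is expressed in multiples of ULN. Nothing in Grade 3 starts where Grade 2 leaves off. Grade 1 gives a single point, and that point is already the lower bound of the Grade 2 limb based on ULN.

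The row sits behind a stopping rule for a drug whose kidney toxicity the protocol describes at length in section 5.1.1. At stake are consistent renal grading across the participating hospitals and the possibility that a participant whose creatinine has more than tripled is not withdrawn, although a smaller rise would have led to withdrawal.

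**Working it through.** There is no stated figure to reproduce, so the check is of the row's logic. Write *b* for baseline creatinine, *v* for the follow-up value and *U* for ULN.

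**Inputs.** The cut-offs are from section 6.3. The documents give no creatinine ULN in mg/dL, because section 3.6.8 uses each laboratory's own normal values. I assume 0.9 to 1.1 mg/dL for women and 1.2 to 1.3 for men. Section 3.2 requires an eGFR of at least 60 and sets no lower limit on creatinine, so low baselines are eligible.

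**1. The Grade 3 limb.** Grade 2 is met if 1.5*b* ≤ *v* ≤ 3*b*, or if 1.5*U* ≤ *v* ≤ 3*U*. Taken as a level, the first Grade 3 limb is 3*U*, which repeats the start of the second limb. Taken as an increment over baseline, it is *b* + 3*U*; for *b*/*U* from 0.4 to 1.0 that is 3.4 to 4.0 x ULN. Neither starts at 3*b*.

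**2. When values fall out of Grade 2.** The window 3*b* < *v* < 1.5*U* is outside both Grade 2 limbs and below Grade 3. It exists when 3*b* < 1.5*U*, that is, when *b* < *U*/2. This condition needs no assumed ULN and does not depend on how Grade 1 is read.

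**3. Example, *b* = 0.50 and *U* = 1.1.** The window runs from 3 x 0.50 = 1.50 to 1.5 x 1.1 = 1.65 mg/dL.

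| Value (mg/dL) | x baseline | x ULN | Grade as printed |
|---|---|---|---|
| 1.20 | 2.4 | 1.09 | 2, withdrawn |
| 1.60 | 3.2 | 1.45 | none, or 1 if Grade 1 means up to 1.5 x ULN; not withdrawn |
| 1.70 | 3.4 | 1.55 | 2, withdrawn |

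The window covers 3.0 to 3.3 x baseline here. At *b* = 0.45 it covers 3.0 to 3.67 x baseline (1.65/0.45).

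**4. Which baselines are exposed.** The limit *U*/2 is 0.45, 0.55, 0.60 and 0.65 mg/dL for *U* = 0.9, 1.1, 1.2 and 1.3. A scan in 0.01 steps from 0.40 mg/dL found a reversal at 5, 15, 20 and 25 baselines respectively. These are grid points, not participants.

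**5. Baselines at or above half of ULN.** There is no reversal, only under-grading. At *b* = 0.8 and *U* = 1.1, values from 2.4 (3*b*) to 3.3 (3*U*) stay Grade 2. At *b* = 0.6 and *U* = 1.2, a fivefold rise to 3.0 mg/dL is 2.5 x ULN and still Grade 2. Withdrawal applies in both cases.

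**6. Grade 1.** As a level, 1.5*U* is exactly the Grade 2 floor. As an increment, *b* + 1.5*U* is 1.9 to 2.5 x ULN for *b*/*U* from 0.4 to 1.0, which lies inside Grade 2. Read either way, values above ULN but below both 1.5*b* and 1.5*U* have no grade: at *b* = 1.0 and *U* = 1.2 that is 1.2 to 1.5 mg/dL. Reading the cell as up to 1.5 x ULN closes this gap.

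**7. Effect of the repair.** With the first Grade 3 limb read as above 3 x baseline, no reversal remained at any baseline or ULN tried, under any reading of Grade 1. At *b* = 0.5 and *U* = 1.2, 1.4 mg/dL is Grade 2, and 1.6 and 1.75 are Grade 3.

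**8. Neighbouring cells.** Grade 1 for ALT and AST prints ">3 x ULN if baseline was normal. 1.5-3 x ULN of baseline if it was not normal"; its first part is the Grade 2 floor. Grade 1 for anemia and lymphocytes is bounded above by ULN, where the platelet row uses the lower limit of normal (LLN). As printed, a normal hemoglobin reads as Grade 1 anemia. No withdrawal rule names these rows.

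**The case against.** The strongest reply is that Grade 3 contains a slip that any clinician would read through. The parallel with Grade 2 points to a stray ULN, the ALT/AST row has a similar one, and with the word removed the reversal disappears. The table also keeps Spanish abbreviations, so the error may come from translation and the text used at the sites may differ. The investigator's manual and operating procedures are not available to check. The double asterisk on the Grade 1 heading has no note in the text available.

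This stands as to intent, and it makes the reversal conditional on the literal wording. It does not make the wording right: this row is the only statement of the creatinine cut-offs in the documents.

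The reply is also right that the consequence is small. Table 1 schedules on-study creatinine at days 40 and 60, and dosing ends at day 60, so a missed stop from a scheduled test leaves at most 20 doses. Section 3.6.8 has a study doctor decide on continuity. Section 6.1 counts an abnormal laboratory finding as an adverse event without requiring a grade, so the Grade 1 gap need not change event counts.

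A reader might infer three stronger points, which the documents do not support:

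- *The scale is unusable.* It is not. The entry points that trigger action, 1.5 x baseline and 1.5 x ULN, are clear.
- *The cited 24-month tenofovir trial, with no creatinine elevation of grade 3 or higher, bounds the frequency.* Its grading scale is not given, and the window here lies below 1.5 x ULN, so it need not be Grade 3 there.
- *The arms would be graded differently.* Section 5.1.1 reports of that trial that "grade 1 and 2 creatinine elevation were not associated with TDF reception", and nothing else in the documents establishes such a difference.

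**Conclusion.** The point holds as two wording errors of minor consequence. Read literally, the Grade 3 cell under-grades rises above 3 x baseline. For baselines below half of ULN, it also lets values between 3 x baseline and 1.5 x ULN escape a withdrawal rule that smaller rises meet. The Grade 1 cell has no range unless it is read as an upper bound.

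A missed withdrawal needs a low baseline, a more than threefold rise that is still below 1.5 x ULN, and a doctor who lets it pass. I expect this to be very rare; no rate can be estimated from the documents. I see no effect on the planned efficacy analyses. None uses the grade, and the one indirect route, censoring at withdrawal, would touch an isolated participant at most. Grades can be re-derived from the recorded mg/dL values.

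The condition on baseline is algebraic. The mg/dL examples rest on the assumed ULNs.

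**What to change.** Replace the creatinine row with:

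- Grade 1: above ULN to 1.5 x ULN.
- Grade 2: above 1.5 to 3 x baseline, or above 1.5 to 3 x ULN.
- Grade 3: above 3 x baseline, or above 3 to 6 x ULN.
- Grade 4: above 6 x ULN.
- The highest grade met applies.

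In the same table, set Grade 1 ALT/AST with a normal baseline to above ULN to 3 x ULN, and replace ULN with LLN in the Grade 1 cells for anemia and lymphocytes. In Appendix 3, the kidney withdrawal flag names grade 2 only; change it to grade 2 or greater, to match section 3.6.9.

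The cost is wording in a few cells and one label. There are no new tests and no change to the analyses. Apart from a value falling exactly on a boundary, the point at which withdrawal begins stays where it is.

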9.1 Technical services

No.	Item	Site	Justification	Quantity	Unit value (cop)	Subtotal (cop)
1	Civil liability policy for volunteers and clinical trial personnel	Pontificia Universidad Javeriana	Regulatory agency requires a liability protection for both, volunteers and clinical trial personnel regarding risks during COVID-19 pandemic.	1	\$ 96,101,872.44	\$ 96,101,872.44
2	Clinical laboratory tests (Creatinine; CBC; ALT; AST; BHCG in women, antiHBS; HIV, IgG Antibodies; Serum phosphorus, CRP)	Pontificia Universidad Javeriana	Laboratory exams required at baseline and follow-up	1	\$ 535,959,372.00	\$ 535,959,372.00
3	rtPCR for symptomatic volunteers (7,5%)	Pontificia Universidad Javeriana	rtPCR for follow-up 1, for volunteers who develop respiratory symptoms (estimated of 7.5%)	71	\$ 250,000.00	\$ 17,750,000.00
4	Laboratories for follow-up 2 (creatinine and antibodies)	Pontificia Universidad Javeriana	Laboratory tests for 950 volunteers	1	\$ 50,071,650.00	\$ 50,071,650.00
5	RtPCR including transport media for follow-up 2.	Pontificia Universidad Javeriana	Laboratory tests. It is estimated that 7.5% of volunteers will develop symptoms that require rtPCR. Services will be provided by recruitment sites	71	\$ 250,000.00	\$ 17,750,000.00
6	Laboratory tests (Creatinine, CBC, ALT, AST, BHCG for women (80% of volunteers) and rtPCR for all subjects.	Pontificia Universidad Javeriana	Laboratory tests for each participant (80% women; 20% men)	1	\$ 285,512,810.00	\$ 285,512,810.00
7	IgG antibody tests for follow up 4	Pontificia Universidad Javeriana	IgG antibody tests for follow up 4	1	\$ 43,320,000.00	\$ 43,320,000.00
8	Recruitment services	Pontificia Universidad Javeriana	Recruitment costs per volunteer including PPE + workhours of pharmaceutical chemist, respiratory therapist, assistant nurse, and laboratory assistant	950	\$ 105,699	\$ 100,414,240
						\$1,146,879,944

9.2 Materials and supplies

No.	Item	Site	Justification	Quantity	Unit value (cop)	Subtotal (cop)
-----	------	------	---------------	----------	---------------------	-------------------

1	IgG antibody tests box (20 kits)	Pontificia Universidad Javeriana	Antibody test for 342 subjects at baseline; 950 for follow-up 1, 475 for follow-up 3 (Brand: Biosensor)	55	\$ 780,000	\$ 42,666,000
2	Placebo; 60 units X 475 volunteers	Pontificia Universidad Javeriana	475 volunteers X 60 days	30000	\$ 200	\$ 6,000,000
3	Investigational drug TDF/FTC	Pontificia Universidad Javeriana	475 volunteers X 60 days	30000	\$ 800	\$ 24,000,000
						\$ 72,666,000

9.3 Total budget

Item	Funded by grant	Pontificia Universidad Javeriana offsetting		Hospital Universitario San Ignacio offsetting		Total
		Cash	In kind	Cash	In kind	
Registry and certification costs	\$0.00	\$0	\$0	\$0	\$0	\$0
Equipment	\$0.00	\$0	\$0	\$0	\$0	\$0
Materials and supplies	\$67,876,084	\$4,789,916	\$0	\$0	\$0	\$ 72,666,000
Scientific staff	\$0.00	\$0	\$18,322,123	\$0	\$172,708,003	\$ 191,030,126
Support staff	\$284,472,000	\$0	\$0	\$0	\$0	\$ 284,472,000
Publications	\$28,000,000	\$0	\$0	\$0	\$0	\$ 28,000,000
Technical support and assistance services	\$23,690,536	\$0	\$0	\$0	\$0	\$ 23,690,536
Technical services	\$1,131,535,948.00	\$15,343,996	\$0	\$0	\$0	\$1,146,879,944
Management (7%)	\$107,490,220	\$0	\$0	\$0	\$0	\$ 107,490,220
CTEI instrument management (5%)	\$82,153,239	\$0	\$0	\$0	\$0	\$ 82,153,239
TOTAL	\$1,725,218,040	\$20,133,912	\$18,322,123	\$0	\$172,708,003	\$1,936,382,066

Appendix 1.

Clinical trials on prophylaxis for COVID-19 with TF/FTC currently registered in ClinicalTrials.gov

Study	Recruitment	Study site	Description and objectives	Outcomes	Design
Clinical Trial for the Prevention of SARS-CoV-2 Infection (COVID-19) in Healthcare Personnel (EPICOS)	Recruiting	Plan Nacional sobre el Sida (PNS), Spain	To evaluate the efficacy of a daily single dose of TDF/FTC (245/200 mg) or a daily single dose of hydroxychloroquine or combination of both vs placebo for prevention of COVID-19. 4000 volunteers will be included assigned to treatment arm in proportion of 1:1:1:1. The length of treatment will be 12 weeks. Follow-up will go on for 4 weeks after completion of treatment. Interim analyses will be performed monthly.	Number of symptomatic serology confirmed SARS-CoV-2 infections. Number of asymptomatic serology confirmed SARS-CoV-2 infections. Severity of COVID-19, determined as follows: - Duration of symptoms. - Relationship between treatment duration and development of symptoms. - Relationship between treatment duration and duration of symptoms. - Seroconversion of IgM/IgG since development of symptoms.	Study type: Clinical trial. Number of participants: 4000. Allocation: randomized. Trial design: parallel. Masking: double. Primary outcome: protection. Estimated recruitment start date: April 1, 2020. Estimated recruitment end date: June 30, 2020. Estimated completion date: July 31, 2020.

TAF/FTC for Pre-exposure Prophylaxis of COVID-19 in Healthcare Workers (CoviPrep Study)- ARGENTINA	Not yet recruiting	Hospital Italiano, Buenos Aires, Argentina	To evaluate the efficacy of TAF/FTC for 12 weeks vs placebo for the prevention of COVID-19 in health care workers.	Number of symptomatic or asymptomatic COVID-19 cases assessed by antibodies and confirmed by rtPCR. Number of asymptomatic serology confirmed COVID-19. Severity of symptoms defined as follows: - Mild: malaise, fever, cough, myalgia, arthralgia. - Moderate: shortness of breath. - Severe: requirement of intensive care. Duration of symptoms. Relationship between treatment and duration of symptoms. Time to seroconversion.	Study type: Clinical trial. Number of participants: 1378 Allocation: randomized. Trial design: parallel Masking: triple. Primary outcome: protection. Estimated recruitment start date: June 15, 2020. Estimated recruitment end date: non specified. Estimated completion date: November 11, 2020
A real-world study for lopinavir/ritonavir (LPV/r) and emtricitabine (FTC) / Tenofovir alafenamide fumarate tablets (TAF) regimen in the treatment of novel coronavirus pneumonia (COVID-19)- CHINA	Not yet recruiting	Sichuan Academy of Medical Sciences & Sichuan Provincial People's Hospital	Real-life study. Non-randomized non-blinded study of treatment of health care professionals with TAF/FTC plus LPV/r vs LPV/r alone. Duration not specified.	Primary outcome: survival rate. Secondary outcomes: -Time to negative rtPCR. -Time to ARDS development. - Hospitalization length.	Study type: real life interventional study. Number of participants: 120. Allocation: non-specified. Masking: no masking. Primary outcome: protection. Estimated recruitment start date: February 2, 2020. Estimated recruitment end date: not specified. Estimated completion date: June 30, 2020.

